5.3.5.2 Clinical Protocol

- The study population for efficacy will include all safety population patients who have baseline and follow-up tumor measurements as required for assessment by RECIST 1.1.

Patients who experience DLT who receive less than the prescribed dose of TRC105 or pazopanib due to documented toxicity in cycle 2 will be considered evaluable for dose escalation purposes.

Only those patients who are deemed "ineligible" or who receive no therapy (i.e. no TRC105 or pazopanib) will be eliminated from the analysis. Ineligible patients who receive therapy will not be included in the assessment of efficacy endpoints, but their data will be included in the assessment of all adverse event reporting.

10.1.2. Phase 2 Statistical Design/Sample Size

Sixty three patients will be treated in the phase 2 portion of the study.

The study population for safety and efficacy will include all patients receiving at least a portion of one dose of TRC105.

Assuming a true median PFS of 4.6 months, a 9-month accrual period, a 6-month follow-up period, and based on the use of a one-sided test at the $\alpha=0.05$ level of significance, a sample size of 63 patients will provide 86% power to detect a 50% increase in the median PFS (i.e., a median of 6.9 months). These power estimates are based on the approach of Lawless [1].

Two additional phase 2 cohorts of up to 13 patients each with angiosarcoma will be enrolled into separate cohorts, angiosarcoma cohort 1 and 2. Angiosarcoma cohort 1: Assuming a 15% response rate by RECIST with pazopanib alone, 5 responders with TRC105 alone or in combination with pazopanib will provide >90% confidence the true response rate is >15% (two-sided exact 90% binomial with 5 of 13 responders is 16.57 and 64.52%). Angiosarcoma cohort 2: Assuming a 15% response rate by RECIST with pazopanib alone, 5 responders with TRC105 in combination with pazopanib will provide >90% confidence that the true response rate is >15%.

For each of the angiosarcoma cohorts, the two-sided exact 90% binomial with 5 of 13 responders is 16.57% and 64.52%.

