5.3.5.2 Clinical Protocol

Probability of Failing to Observe True Underlying DLT Rate at a Dose Level

True Underlying DLT Rate	5%	10%	20%	30%	40%	50%	60%	70%	80%	90%
Probability of Failing to Observe Toxicity, N = 3	0.86	0.73	0.51	0.34	0.22	0.13	0.006	0.027	0.008	0.001
Probability of Failing to Observe Toxicity, N = 6	0.74	0.53	0.26	0.12	0.05	0.016	0.004	<0.001	<0.001	<0.001

Phase 2:

Primary analysis:

The primary analysis will test the null hypothesis that the median PFS is equal to 4.6 months. The time-to-event distribution for PFS will be estimated using the Kaplan-Meier method and the analysis will be based on the two-sided 90% confidence interval for the median (equivalent to the use of a one-sided test at the $\alpha=0.05$ level of significance).

An additional phase 2 cohort of up to 13 patients with angiosarcoma will be enrolled (angiosarcoma cohort 1). Assuming a 15% response rate by RECIST with pazopanib alone, 5 responders with TRC105 alone will provide >90% confidence that the true response rate is >15%.

A second additional phase 2 cohort of up to 13 patients with angiosarcoma will be enrolled (angiosarcoma cohort 2). Assuming a 15% response rate by RECIST with pazopanib alone, 5 responders with TRC105 in combination with pazopanib will provide >90% confidence that the true response rate is >15%.

Sample size justification:

Assuming a true median PFS of 4.6 months, a 9-month accrual period, a 6-month follow-up period, and based on the use of a one-sided test at the $\alpha=0.05$ level of significance, a sample size of 63 patients will provide 86% power to detect a 50% increase in the median PFS (i.e., a median of 6.9 months). For the angiosarcoma cohorts, the two-sided exact 90% binomial with 5 of 13 responders is 16.57% and 64.52%.

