5.3.5.2 Clinical Protocol

Patients in angiosarcoma cohort 1 will initially receive weekly single-agent TRC105 with transition to treatment with the combination of TRC105 and pazopanib at progression per RECIST 1.1.

Patients in angiosarcoma cohort 2 will receive TRC105 in combination with pazopanib starting on cycle 1 day 1.

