5.3.5.2 Clinical Protocol

- Urinalysis to be performed locally. Microscopic analysis and/or urine protein-creatinine ratio (UPCR) should be performed as clinically indicated.
- Phase 1b dose levels -1, 1, 2 and expanded cohort 1 and angiosarcoma cohort 2: Blood sampling for TRC105 pharmacokinetics will include a pre-infusion trough sample and an end-of-infusion peak sample to be analyzed by a third party laboratory (see laboratory manual for specific instructions regarding collection times, procedures, processing, storage and shipment).
- Phase 1b dose levels 3, 4 and expanded cohort 2: Blood sampling for **TRC105 and pazopanib** pharmacokinetics will include trough sample collections to be analyzed by a third party laboratory (see laboratory manual for specific instructions regarding collection times, procedures, processing, storage and shipment).
- Phase 2 including angiosarcoma cohorts: Blood sampling for TRC105 and pazopanib pharmacokinetics will include trough sample collections to be analyzed by a third party laboratory (see laboratory manual for specific instructions regarding collection times, procedures, processing, storage and shipment).
- Blood sampling for immunogenicity to be analyzed by a third party laboratory (see laboratory manual for specific instructions regarding collection, processing, storage and shipment).
- Blood sampling for protein biomarker analysis by a third party laboratory (see laboratory manual for specific instructions regarding collection processing, storage and shipment)
- CT or MRI scans of chest, abdomen and/or pelvis in addition to any other applicable sites of disease. Scan of the chest, abdomen, and pelvis to be performed on-study as outlined in the assessment table. Known areas of disease should be consistently followed throughout the study. Assessments should be performed whenever disease progression is suspected. Allowable window for tumor imaging studies is +/- 7 days. Brain and bone scans to be performed if metastasis is suspected prior to starting the study and during study conduct. Color photography with caliper or ruler measurements should be used to assess cutaneous tumors (target lesions).
 - Patients in angiosarcoma cohort 1 who progress on single agent TRC105 by RECIST, tumor assessments will occur every 6 weeks from the new baseline (ie scans that showed progression on single agent).

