5.3.5.2 Clinical Protocol

21. **Cycle 2+ Treatment: Angiosarcoma cohort 1** patients will be eligible for single-agent TRC105 until progression. At the time of progression by RECIST 1.1 on single-agent TRC105, patients will transition to treatment with the combination of TRC105 and pazopanib. **Angiosarcoma cohort 2** patients will be eligible for treatment with the combination until progression.
22. **Follow-up:** The follow-up visit should occur 28 days following the last dose of TRC105. The allowable visit window is +/- 7 days.
23. Allowable window for each visit within the cycle is +/- 2 days unless otherwise stated.

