7.1.1.1. Recording Tumor Measurements

Measurable lesions up to a maximum of 5 lesions representative of all involved organs (with a maximum of 2 lesions per organ) should be identified as target lesions and measured and recorded at Screening and at the stipulated intervals during treatment. Target lesions should be selected on the basis of their size (lesion with the longest diameters) and their suitability for accurate repetitive measurements (either by imaging techniques or clinically). Target lesions may include lymph nodes with a short axis ≥ 15 mm.

The longest diameter will be recorded for each target lesion (with the exception of lymph nodes, where the short axis will be used). The sum of the diameter for all target lesions at Screening will be calculated and recorded as the baseline sum diameter to be used as reference to further characterize the objective tumor response of the measurable dimension of the disease during treatment. All measurements should be performed using a caliper or ruler and should be recorded in metric notation in millimeters.

All other lesions (or sites of disease) should be identified as non-target lesions and should also be recorded at baseline. Measurements are not required and these lesions should be followed as “present”, “stable”, “absent”, “increased” or “decreased”.

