7.1.2. Definitions of Tumor Response

7.1.2.1. Target Lesions

- **Complete response (CR)** is defined as the disappearance of all target lesions.
- **Partial response (PR)** is defined as a $\geq 30\%$ decrease in the sum of the dimensions of the target lesions taking as a reference the baseline sum dimensions.
- **Progressive disease (PD)** is defined as a $\geq 20\%$ relative increase and ≥ 5 mm absolute increase in the sum of the dimensions of the target lesions taking as a reference the smallest sum of the dimensions recorded since the treatment started, or the appearance of one or more new lesions.
- **Stable disease (SD)** is defined as neither sufficient shrinkage to qualify for PR nor sufficient increase to qualify for PD taking as a reference the smallest sum of the dimensions since the treatment started.

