10.2.1.2. Phase 2 Analysis of Primary Objective

The primary analysis will test the null hypothesis that the median PFS is equal to 4.6 months. The time-to-event distribution for PFS will be estimated using the Kaplan-Meier method and the analysis will be based on the two-sided 90% confidence interval for the median (equivalent to the use of a one-sided test at the $\alpha=0.05$ level of significance).

Additional exploratory analyses of PFS will be conducted in subgroups defined based on number of prior therapies (one versus two or more), histology, and endoglin expression on sarcoma tissue.

For the angiosarcoma cohorts, the overall response rate and median duration of response by RECIST 1.1 will be calculated and the response rate will include the two-sided 90% confidence interval.

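### The 5-of-13 response benchmark for angiosarcoma cohort 1 counts responders on TRC105 alone in the synopsis, but responders on TRC105 alone or with pazopanib in Section 10.1.2

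*Combined protocol and SAP*

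**What the plan says.** The angiosarcoma ORR is a phase 2 primary objective (Section 3.2.2). For cohort 1 the benchmark appears twice, with the same maximum of 13 patients and the same 15% pazopanib-alone reference rate:

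- Synopsis, statistical methods for phase 2: "5 responders with TRC105 alone will provide >90% confidence that the true response rate is >15" percent.
- Section 10.1.2: "5 responders with TRC105 alone or in combination with pazopanib will provide >90% confidence the true response rate is >15" percent.

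The treatment sequence is set out in Section 2.6.2: "Patients in angiosarcoma cohort 1 will initially receive weekly single-agent TRC105 with transition to treatment with the combination of TRC105 and pazopanib" at RECIST progression. Footnote 21 to Table 7 agrees: "At the time of progression by RECIST 1.1 on single-agent TRC105, patients will transition to treatment with the combination of TRC105 and pazopanib". After that switch, Section 4.1.2.2 states that "tumor assessments will occur every 6 weeks from the new baseline (ie scans that showed progression on single agent").

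The analysis text for the objective, Section 10.2.1.2, gives one rule for both cohorts: "For the angiosarcoma cohorts, the overall response rate and median duration of response by RECIST 1.1 will be calculated", with a two-sided 90% interval for the response rate. It does not say which phase counts in cohort 1.

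The general response rules are in Section 7.1. On the reference measurement: "The sum of the diameter for all target lesions at Screening will be calculated and recorded as the baseline sum diameter". Partial response is judged "taking as a reference the baseline sum dimensions". Best overall response runs from the start of treatment to progression (Section 7.1.2.3.1), and Section 10.2.3 lists one best response per patient.

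**The concern.** Cohort 1 produces response data in two successive phases: TRC105 alone, then TRC105 plus pazopanib in patients who have progressed. Whether a response in the second phase counts toward the 5 is therefore a real choice in this cohort, and the plan gives two answers.

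The comparator makes the choice matter. The 15% is a rate for pazopanib alone. If both phases are pooled, a patient has two opportunities to respond, the second on a regimen that contains pazopanib. Reaching 5 of 13 that way would show that a cumulative rate over two regimens exceeds 15%. It would not show that TRC105 alone does, or that either regimen does by itself. Section 2.3 gives possible responsiveness to single-agent TRC105 as the reason for studying this subtype that way, and cohort 2 already tests the combination from the first day.

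The trial is open-label with at most 13 patients in the cohort. Leaving the definition open until responses are known would allow it to be chosen with the data in view.

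**Working it through.** **Inputs.** n = 13 (cohort maximum, synopsis and Section 10.1.2); reference rate 15%; two-sided exact 90% interval, 5% in each tail (Sections 10.1.2 and 10.2.1.2).

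**Formula.** For r responders among n, the Clopper-Pearson limits are

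- lower = 5th percentile of Beta(r, n − r + 1), taken as 0 when r = 0
- upper = 95th percentile of Beta(r + 1, n − r)

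**Step 1: the plan's own figure.** With r = 5, the lower limit is the 5th percentile of Beta(5, 9) = 16.57% and the upper limit is the 95th percentile of Beta(6, 8) = 64.52%. Both match the plan. The exact chance of 5 or more responders in 13 at a true rate of 15% is 0.034.

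**Step 2: the smallest count that passes.** With r = 4 the lower limit is 11.3%, below 15%. So 5 is the smallest passing count at n = 13.

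**Step 3: one set of patients under both wordings, with Section 10.1.2 read as pooling.** Suppose 5 patients respond in either phase: s on TRC105 alone, and 5 − s different patients only on the combination.

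| s (TRC105 alone) | Synopsis count | Exact 90% interval | Synopsis benchmark | Pooled count | Pooled benchmark |
|---|---|---|---|---|---|
| 5 | 5/13 | 16.57% to 64.52% | met | 5/13 | met |
| 4 | 4/13 | 11.3% to 57.3% | missed | 5/13 | met |
| 3 | 3/13 | 6.6% to 49.5% | missed | 5/13 | met |
| 2 | 2/13 | 2.8% to 41.0% | missed | 5/13 | met |
| 1 | 1/13 | 0.4% to 31.6% | missed | 5/13 | met |
| 0 | 0/13 | 0% to 20.6% | missed | 5/13 | met |

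Responders on TRC105 alone are a subset of responders in either phase. The disagreement therefore runs one way: a cohort can meet Section 10.1.2 and miss the synopsis, never the reverse.

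**Step 4: the other reading of Section 10.1.2.** The phrase may instead mean 5 of 13 on either regimen, tallied separately. The 4 + 1 split then reaches 5 on neither. But 5 responders on the combination with fewer than 5 on TRC105 alone would still meet Section 10.1.2 and miss the synopsis.

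**Step 5: illustration under an assumption the documents do not supply.** Let the true rate on TRC105 alone be exactly 15%, and let a fraction q of the remaining patients respond on the combination. The either-phase rate is p = 1 − (1 − 0.15)(1 − q).

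| q | p | P(at least 5 of 13, either phase) |
|---|---|---|
| 0 | 15.00% | 0.034 |
| 5% | 19.25% | 0.087 |
| 10% | 23.50% | 0.170 |
| 15% | 27.75% | 0.280 |

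Counting TRC105 alone, the probability stays at 0.034 throughout. The rise is not an error in the interval, because the either-phase rate really is above 15% when q > 0. It shows how far a pooled result can move with no gain in single-agent activity.

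**Step 6: what the general rules imply.** The screening reference sum and a best-response window that closes at progression both point to the single-agent phase in cohort 1, in agreement with the synopsis. The cohort-specific statement that progression means progression on the combination (Section 5.3) concerns withdrawal from treatment, so it does not reopen that window.

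**The case against.** The strongest reply is that the protocol already settles the matter. The general response rules favour the single-agent phase, as the synopsis does, which leaves one stray phrase in a sample-size paragraph. That phrase can be read as two separate tallies. Section 2.3 lends this some support, since it says the angiosarcoma cohorts evaluate TRC105 both as a single agent and in combination. The objective is to estimate a rate; no test, stopping rule or go/no-go decision uses the 5-of-13 figure. The table fixes the pooled total at exactly 5, where moving one responder must change the result. It also assumes full enrolment, although the cohort is up to 13: with 9 patients, for example, 4 responders give a lower limit of 16.9%. Finally, the documents do not say which wording was intended.

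Much of this stands. The reversal with a single moved responder depends on the pooled reading and on n = 13, no decision rule is affected, and with 5 or more single-agent responders both wordings are met. Two points remain. First, the general rules are not written for cohort 1, Section 4.1.2.2 introduces a new baseline after the switch, and Section 10.2.1.2 names no phase, so nothing expressly overrides Section 10.1.2. Second, separate tallies would still give cohort 1 a combination benchmark that the synopsis lacks. Any reading that gives effect to the extra words conflicts with the synopsis.

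**Conclusion.** The concern holds. The plan defines the cohort 1 benchmark in two incompatible ways in current text, and the section an analyst would consult for it departs from both the synopsis and the general response definition. The 5-of-13 arithmetic is right; the definition of a responder is not fixed. With 13 patients and a pooled reading, every split of 5 responders with 0 to 4 on TRC105 alone meets Section 10.1.2 and misses the synopsis. That comparison needs no assumed response rate. The probabilities in Step 5 do rest on assumed rates and are illustrative only. No combination-phase rate can be given, because the documents do not say how many patients will transition.

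The consequence is limited to attribution and interpretation of a primary estimate. An exact interval for an either-phase count is valid for that cumulative rate, but it does not answer the single-agent question. This should be fixed before the cohort is analysed.

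**What to change.** 1. In the cohort 1 sentence of Section 10.1.2, delete the words that extend the count to the combination, so that it matches the synopsis.
2. Add to Section 10.2.1.2: *For angiosarcoma cohort 1, the primary ORR, to which the 5-of-13 benchmark applies, counts confirmed CR or PR on single-agent TRC105 relative to the screening baseline and before first RECIST progression. Responses after transition to the combination are assessed relative to the transition baseline and reported separately with their own exact 90% interval.*

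The new sentence also settles a point now left to inference: Section 4.1.2.2 uses the new baseline to time scans, while Section 7.1 defines response against screening only. If the sponsor did intend an either-phase rate, it should say so in both places and describe the result as a cumulative rate over two regimens.

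The cost is one deletion and a short addition. The scans needed are already scheduled, and no treatment or withdrawal rule changes. The drawback is that fewer responses can count toward the cohort 1 benchmark.

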10.1.2.1. Definition of Analyzed Study Populations

The following study populations will be considered when reporting study results for the phase 2 portion:

- The study population for safety includes all patients receiving at least a portion of 1 dose of TRC105.
- The study population for efficacy will include all safety population patients who have baseline and follow-up tumor measurements as required for assessment by RECIST 1.1.

Only those patients who are deemed "ineligible" or who receive no therapy (i.e., no TRC105 or pazopanib) will be eliminated from the analysis. Ineligible patients who receive therapy will not

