5.3.5.2 Clinical Protocol

A formally chartered Safety Review Team will review safety data. In addition, recurring teleconferences will be held with Investigators at all clinical sites.

Pharmacokinetics:

Serum TRC105 concentrations will be measured using validated methods at the time points specified in the Schedule of Events.

Immunogenicity:

Anti-product antibodies will be measured using validated methods at time points specified in the Schedule of Events.

Exploratory Biomarkers:

Concentrations of a panel of angiogenic protein biomarkers in plasma will be measured at baseline and during treatment to explore TRC105 pharmacodynamics.

Efficacy:

RECIST 1.1 will be applied to measurable disease to assess response and progression. Tumor markers will also be evaluated where available.

Archival Tumor Specimens:

Endoglin expression on archival tumor specimens will be correlated with efficacy endpoints (e.g., PFS and ORR).

Statistical methods:Evaluable Study Population:

The study population for safety and efficacy includes all patients receiving at least a portion of 1 dose of TRC105.

The number of patients to be enrolled in this study will depend upon the observed safety profile, which will determine the number of patients per dose level and the number of dose escalations. It is anticipated that a total of up to 30 patients will be treated in the phase 1b portion and 89 patients will be treated in the phase 2 portion.

Phase 1:

The probability of escalation to the next higher dose for each underlying true DLT rate is shown in the table below. For example, for a toxicity that occurs in 5% of patients, there is a > 95% probability of escalating. Conversely, for a common toxicity that occurs with a rate of 70%, the probability of escalating is < 5%.

Probability of Escalation to the Next Dose for Each True Underlying DLT Rate at a Dose Level

True Underlying DLT Rate	5%	10%	20%	30%	40%	50%	60%	70%	80%	90%
Probability of Escalating Dose	0.97	0.91	0.71	0.49	0.31	0.17	0.08	0.03	0.01	0.001

The probability of failing to observe toxicity in a sample size of 3 or 6 patients given various true underlying toxicity rates is shown in the table below. For example, with 6 patients, the probability of failing to observe toxicity occurring at least 40% of the time is < 5%.

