5.3.5.2 Clinical Protocol

7. ASSESSMENT OF EFFICACY

7.1. Radiological Tumor Assessment

The primary efficacy endpoint for phase 2 is PFS, defined as time from screening to either first disease progression or death from any cause per RECIST version 1.1 [68]. Patients alive at the time of analysis will be censored at the date of last disease assessment.

The primary efficacy assessment will be best overall response as defined in Section 7.1.2. The determination of antitumor efficacy will be based on objective tumor assessments made by the Investigator according to RECIST version 1.1 [68]. Investigators will make treatment decisions based on these assessments. All lesions will be classified as target or non-target lesions at the Screening visit. Each lesion designation will be maintained through the course of the study.

The same method and technique should be used to characterize each identified and reported lesion at Screening, during the study treatment period, and at the End of Study visit. Imaging-based evaluation over clinical examination is the required technique when both could be used to assess the antitumor effect of the treatment. Clinical Oncology review of all tumor measurements is desired.

Whenever possible, clinical evaluation of superficial lesions should not be used as the sole form of measurement. However, when necessary, color photograph with metric caliper is acceptable. Tumor evaluation by positron emission tomography (PET) scan or by ultrasound may not substitute for CT or MRI scans.

Radiological tumor assessments will be performed at screening, as outlined in the Schedule of Assessments (Table 4, Table 5, Table 6 and Table 7), and whenever disease progression is suspected. Another tumor assessment will be performed at the End of Study Visit if an assessment has not been performed within the prior 8 weeks. All patient files and radiological images must be available for CRF source verification.

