5.3.5.2 Clinical Protocol

be included in the assessment of efficacy endpoints, but their data will be included in the assessment of all adverse event reporting.

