5.3.5.2 Clinical Protocol**10.2.3. Objective Response**

The best response (CR, PR, SD or PD according to RECIST 1.1) for each patient with measurable disease who received at least one dose of TRC105 study drug will be listed by cohort. Stable disease will be defined as lack of tumor progression lasting for 2 cycles or longer.

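### The phase 2 efficacy population is defined in conflicting ways, and the version requiring a follow-up scan would delete early deaths from PFS and unscanned patients from the ORR denominator

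*Combined protocol and SAP*

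**What the plan says.** Three rules cover the same phase 2 analysis.

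- **All treated.** Section 10.1.2 states: "The study population for safety and efficacy will include all patients receiving at least a portion of one dose of TRC105". The synopsis, under Statistical methods, agrees: "The study population for safety and efficacy includes all patients receiving at least a portion of 1 dose of TRC105".
- **Scan-evaluable.** The second bullet of Section 10.1.2.1 states: "The study population for efficacy will include all safety population patients who have baseline and follow-up tumor measurements", with the qualifier that these are the measurements RECIST 1.1 assessment needs.
- **Eligible and treated.** The paragraph below that bullet says that only patients judged ineligible "or who receive no therapy (i.e., no TRC105 or pazopanib) will be eliminated from the analysis". It adds that ineligible patients who were treated will not "be included in the assessment of efficacy endpoints, but their data will be included in the assessment of all adverse event reporting".

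Section 10.2.3 provides that best response "for each patient with measurable disease who received at least one dose of TRC105 study drug will be listed by cohort", with no follow-up scan required. Section 10.2.1.2, which sets out the PFS test and the angiosarcoma response rate, names no population. Section 7.1 has PFS "defined as time from screening to either first disease progression or death from any cause per RECIST version 1.1", so a death before any scan is an event.

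**The concern.** Nothing says which rule governs. The third rule contradicts the second, because a patient without a follow-up scan is neither ineligible nor untreated. It also contradicts the first, because it removes ineligible treated patients from efficacy.

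Measurable disease is already inclusion criterion 4, so the working part of the bullet is the follow-up scan. Membership then depends on something that happens after treatment starts. For PFS, the patients lost who matter are those who die before that scan, and these are among the earliest events. For ORR, a patient with no follow-up scan cannot be a documented responder, so only non-responders are removed.

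The trial has no control arm in which the same selection could offset this. PFS is tested against a fixed 4.6 months and ORR is read against 15%. Leaving the set open also allows it to be chosen after open-label data have been seen.

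Unscanned patients are foreseeable. The first routine scan in the soft tissue sarcoma group is at cycle 2 day 22, which is day 28 + 22 = 50 (Table 6), and in the angiosarcoma cohorts at 6 weeks (Table 7). Section 7.1 says of the final scan: "Another tumor assessment will be performed at the End of Study Visit if an assessment has not been performed within the prior 8 weeks". Read literally, a screening scan can satisfy that. Scans prompted by suspected progression lower the number of unscanned patients but cannot bring it to zero.

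**Working it through.** **Inputs.** From Section 10.1.2: n = 63, null median 4.6 months, alternative 6.9 months, accrual 9 months, follow-up 6 months, one-sided α = 0.05, and 13 patients per angiosarcoma cohort read against 15%. From Section 10.2.1.2: the test uses the two-sided 90% confidence interval for the Kaplan-Meier median. Assumed, because the documents give no figure: k, the number of deaths before any follow-up scan, set at 1, 3 and 6 of 63 (1.6%, 4.8% and 9.5%).

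**The plan's own figures reproduce on the full numbers.** With exponential PFS and uniform accrual, expected events among 63 are 49.0 under the null and 40.3 under the alternative. Power = Φ[(ln 1.5 − 1.645/√49.0) × √40.3] = 86.1%, against the stated 86%. The exact 90% interval for 5/13 is 16.57% to 64.52%, as stated. Both figures assume that nobody is dropped.

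**PFS, type I error.** Minimum follow-up (6 months) exceeds 4.6 months. With no earlier censoring, the number of events by 4.6 months under the null is X ~ Bin(63, 0.5). Dropping k early deaths leaves X − k events in 63 − k patients. The test rejects when the lower 90% limit of S(4.6) exceeds 0.5. The plan does not name the type of limit, so both common Greenwood forms are shown.

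| k dropped | Reject if events ≤ (log-log / plain) | Same cut-off in X of 63 | Type I error (log-log / plain) | Apparent median, months |
|---|---|---|---|---|
| 0 | 24 / 25 of 63 | 24 / 25 | 3.9% / 6.5% | 4.60 |
| 1 | 24 / 24 of 62 | 25 / 25 | 6.5% / 6.5% | 4.71 |
| 3 | 23 / 23 of 60 | 26 / 26 | 10.4% / 10.4% | 4.92 |
| 6 | 21 / 22 of 57 | 27 / 28 | 15.7% / 22.5% | 5.26 |

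The apparent median is −ln[0.5(1 − k/63)] × 4.6/ln 2. For k = 3: −ln(0.5 × 60/63) × 4.6/0.6931 = 4.92.

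A simulation of 20,000 trials with the planned accrual and follow-up, dropping 3 random events before day 50, gave 10.5% for both types of limit. A second simulation removed a random share of patients as early deaths and used log-log limits. It gave 6.7% at a 3% share, 9.1% at 5% and 17.8% at 10%, against about 4% with all treated patients kept.

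**One data set, two answers.** Suppose 26 of 63 patients have events by 4.6 months. S(4.6) = 37/63 = 0.587, with lower limits 0.478 (log-log) and 0.485 (plain), so 4.6 months is not rejected. Remove 3 unscanned deaths: 23 of 60, S(4.6) = 37/60 = 0.617, with lower limits 0.505 and 0.513. Now it is rejected under both.

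**ORR.** Four responders, with unscanned patients removed from the denominator (exact 90% lower limit):

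| Denominator | ORR | Lower limit |
|---|---|---|
| 13 | 30.8% | 11.3% |
| 12 | 33.3% | 12.3% |
| 11 | 36.4% | 13.5% |
| 10 | 40.0% | 15.003% |

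The chance of 5 or more responders among 13 at a true 15% is 3.4%, and this does not depend on the denominator used.

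**The case against.** The strongest reply is that the bullet's closing words tie it to RECIST assessment. It could then be meant only as a response-evaluable set, leaving PFS deaths to Section 7.1. That reading is possible but not secure: the bullet says efficacy without limit, and Section 7.1 places PFS under RECIST as well. The possibility shows that the text needs settling.

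Several narrower points stand:

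- Section 10.2.3 is a listing rule and sets no ORR denominator, so the conflict rests mainly on Section 10.1.2 and the synopsis against Section 10.1.2.1.
- Section 4.1.3 words the scan waiver as the last 8 weeks on study, under which a screening scan arguably does not count. The waiver mainly concerns living patients. They are not PFS events without progression, and removing them does not bias the Kaplan-Meier estimate, so it bears on ORR.
- The plain-limit error is already 6.5% with nobody dropped, and one dropped death leaves it there. Only the increase over each method's own starting value belongs to this point.
- The stated criterion of 5 responders is a count and is unaffected. With 4 responders, the lower limit passes 15% only when 3 of 13 are unscanned, and then barely. ORR alone would be a minor matter.

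**Conclusion.** The concern holds. The population for the primary test is not uniquely defined, and one of the written rules biases PFS and ORR upward. The direction follows from the definitions. The size rests on the assumed number of early unscanned deaths and, for the closed-form figures, on no censoring before 4.6 months. Three such deaths among 63 add 6.5 percentage points to the type I error with log-log limits (3.9% to 10.4%) or 3.9 points with plain limits (6.5% to 10.4%), and can reverse the primary conclusion. If every patient has a follow-up scan, the bullet does no harm, but the conflict over ineligible treated patients remains. This should be corrected before the analysis.

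**What to change.** Amend Section 10.1.2.1 as follows.

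1. Make the all-treated set of Section 10.1.2 and the synopsis the primary efficacy population for PFS and ORR, and name it in Section 10.2.1.2.
2. Count deaths before the first post-baseline scan as PFS events.
3. Censor living patients with no post-baseline scan at the PFS time origin. Section 7.1 says only that time runs from screening, which may span 28 days, so state the date; the baseline tumor assessment fits that section.
4. Count unscanned patients as non-responders in the ORR.
5. Keep the scan-evaluable set as a labelled sensitivity analysis.
6. Reconcile the exclusion of ineligible treated patients with Section 10.1.2, for example as a second sensitivity analysis with eligibility decided before outcomes are reviewed.

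The cost is a wording amendment with no new data. The PFS and ORR estimates may come out slightly less favourable. The same bullet stands in Section 10.1.1.1 for phase 1b and can be aligned at the same time.
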